16.4 Appendix 4: ESSDAI

Table 16-5 The EULAR Sjögren's syndrome disease activity index (ESSDAI): domain and item definitions and weights

Domain [weight]	Activity level	Description
Constitutional [3] Exclusion of fever of infectious origin and voluntary weight loss	No = 0 Low = 1 Moderate = 2	Absence of the following symptoms Mild or intermittent fever (37.5–38.5°C)/night sweats and/or involuntary weight loss of 5-10% of body weight Severe fever (>38.5°C)/night sweats and/or involuntary weight loss of >10% of body weight
Lymphadenopathy [4] Exclusion of infection	No = 0 Low = 1 Moderate = 2 High = 3	Absence of the following features Lymphadenopathy ≥1 cm in any nodal region or ≥2 cm in inguinal region Lymphadenopathy ≥2 cm in any nodal region or ≥3 cm in inguinal region, and/or splenomegaly (clinically palpable or assessed by imaging) Current malignant B-cell proliferative disorder
Glandular [2] Exclusion of stone or infection	No = 0 Low = 1 Moderate = 2	Absence of glandular swelling Small glandular swelling with enlarged parotid (≤3 cm), or limited submandibular or lachrymal swelling Major glandular swelling with enlarged parotid (>3 cm), or important submandibular or lachrymal swelling
Articular [2] Exclusion of osteoarthritis	No = 0 Low = 1 Moderate = 2 High = 3	Absence of currently active articular involvement Arthralgias in hands, wrists, ankles and feet accompanied by morning stiffness (>30 min) 1–5 (of 28 total count) synovitis ≥6 (of 28 total count) synovitis

Domain [weight]	Activity level	Description
Cutaneous [3] Rate as 'no activity' stable long-lasting features related to damage	No = 0 Low = 1 Moderate = 2 High = 3	Absence of currently active cutaneous involvement Erythema multiforma Limited cutaneous vasculitis, including urticarial vasculitis, or purpura limited to feet and ankle, or subacute cutaneous lupus Diffuse cutaneous vasculitis, including urticarial vasculitis, or diffuse purpura, or ulcers related to vasculitis
Pulmonary* [5] Rate as 'no activity' stable long-lasting features related to damage, or respiratory involvement not related to the disease (tobacco use, etc)	No = 0 Low = 1 Moderate = 2 High = 3	Absence of currently active pulmonary involvement Persistent cough or bronchial involvement [^] with no radiographic abnormalities on radiography Or radiological or HRCT evidence of interstitial lung disease with no breathlessness and normal lung function test Moderately active pulmonary involvement, such as interstitial lung disease shown by HRCT with shortness of breath on exercise (NYHA II) or abnormal lung function tests restricted to 70% > DL _{co} ≥ 40% or 80% > FVC ≥ 60% Highly active pulmonary involvement, such as interstitial lung disease shown by HRCT with shortness of breath at rest (NYHA III, IV) or with abnormal lung function tests DL _{co} < 40% or FVC < 60%

Domain [weight]	Activity level	Description
Renal [5] Rate as 'no activity' stable long-lasting features related to damage and renal involvement not related to the disease. If biopsy has been performed, please rate activity based on histological features first	No = 0 Low = 1 Moderate = 2 High = 3	Absence of currently active renal involvement with proteinuria <0.5 g/day, no haematuria, no leucocyturia, no acidosis, or long-lasting stable proteinuria due to damage Evidence of mild active renal involvement, limited to tubular acidosis without renal failure or glomerular involvement with proteinuria (between 0.5 and 1 g/day) and without haematuria or renal failure (GFR ≥60 ml/min) Moderately active renal involvement, such as tubular acidosis with renal failure (GFR <60 ml/min) or glomerular involvement with proteinuria between 1 and 1.5 g/day and without haematuria or renal failure (GFR ≥60 ml/min) or histological evidence of extra-membranous glomerulonephritis or important interstitial lymphoid infiltrate Highly active renal involvement, such as glomerular involvement with proteinuria >1.5 g/day or haematuria or renal failure (GFR <60 ml/min), or histological evidence of proliferative glomerulonephritis or cryoglobulinaemia-related renal involvement
Muscular* [6] Exclusion of weakness due to corticosteroids	No = 0 Low = 1 Moderate = 2 High = 3	Absence of currently active muscular involvement Mild active myositis shown by abnormal EMG or biopsy with no weakness and creatine kinase (N<CK≤2N) Moderately active myositis confirmed by abnormal EMG or biopsy with weakness (maximal deficit of 4/5), or elevated creatine kinase (2N<CK≤4N) Highly active myositis shown by abnormal EMG or biopsy with weakness (deficit ≤3/5) or elevated creatine kinase (>4N)
PNS* [5]	No = 0 Low = 1	Absence of currently active PNS involvement

Domain [weight]	Activity level	Description
Rate as 'no activity' stable long-lasting features related to damage or PNS involvement not related to the disease	Moderate = 2 High = 3	Mild active peripheral nervous system involvement, such as pure sensory axonal polyneuropathy shown by NCS or trigeminal (V) neuralgia Moderately active peripheral nervous system involvement shown by NCS, such as axonal sensorimotor neuropathy with maximal motor deficit of 4/5, pure sensory neuropathy with presence of cryoglobulinemic vasculitis, ganglionopathy with symptoms restricted to mild/moderate ataxia, inflammatory demyelinating polyneuropathy (CIDP) with mild functional impairment (maximal motor deficit of 4/5 or mild ataxia) Or cranial nerve involvement of peripheral origin (except trigeminal (V) neuralgia) Highly active PNS involvement shown by NCS, such as axonal sensorimotor neuropathy with motor deficit $\leq 3/5$, peripheral nerve involvement due to vasculitis (mononeuritis multiplex, etc), severe ataxia due to ganglionopathy, inflammatory demyelinating polyneuropathy (CIDP) with severe functional impairment: motor deficit $\leq 3/5$ or severe ataxia
CNS* [5] Rate as 'no activity' stable long-lasting features related to damage or CNS involvement not related to the disease	No = 0 Moderate = 2 High = 3	Absence of currently active CNS involvement Highly active CNS features, such as cerebral vasculitis with cerebrovascular accident or transient ischaemic attack, seizures, transverse myelitis, lymphocytic meningitis, multiple sclerosis-like syndrome with motor deficit

Domain [weight]	Activity level	Description
Haematological [2] For anaemia, neutropenia, and thrombopenia, only autoimmune cytopenia must be considered Exclusion of vitamin or iron deficiency, drug-induced cytopenia	No = 0 Low = 1 Moderate = 2 High = 3	Absence of auto-immune cytopenia Cytopenia of auto-immune origin with neutropenia (1000<neutrophils<1500/mm ³), and/or anaemia (10<haemoglobin<12 g/dl), and/or thrombocytopenia (100000<platelets<150000/mm ³) Or lymphopenia (500<lymphocytes<1000/mm ³) Cytopenia of auto-immune origin with neutropenia (500≤neutrophils≤1000/mm ³), and/or anaemia (8≤haemoglobin≤10 g/dl), and/or thrombocytopenia (50000≤platelets≤100000/mm ³) Or lymphopenia (≤500/mm ³) Cytopenia of auto-immune origin with neutropenia (neutrophils <500/mm ³), and/or or anaemia (haemoglobin <8 g/dl) and/or thrombocytopenia (platelets <50000/mm ³)
Biological [1]	No = 0 Low = 1 Moderate = 2	Absence of any of the following biological features Clonal component and/or hypocomplementaemia (low C4 or C3 or CH50) and/or hypergammaglobulinaemia or high IgG level between 16 and 20 g/l Presence of cryoglobulinaemia and/or hypergammaglobulinaemia or high IgG level >20 g/l, and/or recent onset hypogammaglobulinaemia or recent decrease of IgG level (<5 g/l)

^ Based on the EULAR ESSDAI user guide ([Seror et al 2015](#)), an inconsistency was observed under the pulmonary domain. The description column of the low disease activity for the pulmonary domain has been modified from “persistent cough or bronchial involvement” to “persistent cough due to bronchial involvement”.

Commercially Confidential Information

Commercially Confidential Information

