5.1 Inclusion criteria

Subjects eligible for inclusion in this study have to fulfill all of the following criteria at the time of screening evaluations unless otherwise noted.

1. Signed informed consent must be obtained before any study assessment is performed.
2. Male or female patients aged 18 to 75 years
3. Classification of Sjögren's Syndrome according to the 2016 ACR/EULAR criteria ([Shiboski et al 2017](#)).
4. Screening ESSDAI (based on weighted score) ≥ 5 derived from 8 domains (biologic, hematologic, articular, cutaneous, glandular, lymphadenopathy, renal, constitutional). Subjects with involvement of one or more of the remaining 4 domains are eligible but scores of these domains will not contribute to the assessment for eligibility, but will be part of the overall ESSDAI for that subject.
5. Screening ESSPRI ≥ 5
6. Seropositive for anti-Ro/SSA antibodies at or within 3 months prior to screening
7. Unstimulated whole salivary flow rate of > 0 mL/min.
8. Able to communicate well with the Investigator to understand and comply with the requirements of the study.

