8.3.1 EULAR Sjögren's Syndrome Disease Activity Index (ESSDAI)

ESSDAI ([Section 16.4](#)) is a validated disease outcome measure for Sjögren's Syndrome that will be applied to the study subjects. The instrument contains 12 organ-specific domains contributing to disease activity. For each domain, features of disease activity are scored in 3 or 4 levels according to their severity. These scores are then summed across the 12 domains in a weighted manner to provide the total score. The domains (weights) are as follows: constitutional (3), lymphadenopathy (4), glandular (2), articular (2), cutaneous (3), pulmonary (5), renal (5), muscular (6), PNS (5), CNS (5), hematological (2), and biological (1). The maximum possible score is 123.

To calculate ESSDAI, all 12 organ domains must be individually assessed at every scheduled timepoint (from screening visit till end of study). Domain assessments will be entered into a tablet (provided by a central vendor) and ESSDAI score will be calculated by the software. At screening, the ESSDAI subscore from 8 pre-selected domains listed in the inclusion criterion #7, will be calculated to determine patient's eligibility.

For assessments not listed in the protocol as mandatory tests but which may be needed to estimate ESSDAI, including radiography, high resolution computer tomography (HRCT), lung function test (DLCO, FVC), estimated glomerular filtration rate (eGFR), electromyography (EMG), muscle (or any other) biopsy, it is at the investigator's discretion to have these assessed based on the signs and symptoms of the patient so to provide correct ESSDAI readout.

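### Does the uncorrected pulmonary cell in the ESSDAI table (cough *or* versus cough *due to* bronchial involvement) call for a change to the plan?

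*Protocol*

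**What the plan says.** Protocol Section 16.4, Table 16-5, gives the pulmonary domain weight 5 and activity levels 0 to 3. There are two routes to Low (level 1). One is "Persistent cough or bronchial involvement" with a clear radiograph, and this phrase carries a caret. The other is interstitial lung disease on imaging without breathlessness and with normal lung function. Level 0 is defined as "Absence of currently active pulmonary involvement". The row also tells raters to score as inactive any stable long-standing damage, or "respiratory involvement not related to the disease (tobacco use, etc").

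The caret footnote belongs to the same table. It reports an inconsistency noticed against the published ESSDAI user guide and states that "The description column of the low disease activity for the pulmonary domain has been modified". It quotes the *or* wording as the text before modification and "persistent cough due to bronchial involvement" as the text after.

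Three other places bear on the point:
- Protocol Section 5.1, criterion 4, bases entry on eight domains that do not include pulmonary. For the other four, "scores of these domains will not contribute to the assessment for eligibility", although they "will be part of the overall ESSDAI for that subject".
- Protocol Section 8.3.1 says "Domain assessments will be entered into a tablet (provided by a central vendor) and ESSDAI score will be calculated by the software".
- SAP Section 2.5.2 uses total ESSDAI for the primary change score, as a continuous baseline covariate and as the <10 / ≥10 model factor.

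**The concern.** The footnote describes an edit that the cell does not show. PDF reading does not explain this, because the footnote prints both wordings and the cell matches the replaced one. The footnote is attached to the current table, so it is not an amendment log either, and nothing here is redacted.

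The difference is one of substance. *Or* accepts either feature alone, while *due to* requires a cough with a bronchial cause. A rater working from the cell and a rater working from the footnote could disagree about two kinds of patient: one with a disease-related persistent cough but no bronchial involvement, and one with bronchial involvement but no persistent cough.

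The domain weight is 5 and the score feeds the primary endpoint. If different raters, or the same rater at different visits, used different wordings, a stable finding could appear as a change of up to 5 points in either direction. A baseline rating could also move a patient across the stratum cut at 10.

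**Working it through.** **Inputs**
- Pulmonary weight 5: Table 16-5 and Protocol 8.3.1.
- Domain score = activity level × weight, summed over twelve domains: SAP 2.5.1.
- Expected 24 patients per group: SAP 1.1.
- Primary contrast, qd and bid averaged against placebo: SAP 1.2.1 and 2.5.2.
- Minimum eight-domain entry score 5: Protocol 5.1.

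**Step 1: reproduce the plan's own figure.** Weight × highest level, in the order constitutional, lymphadenopathy, glandular, articular, cutaneous, pulmonary, renal, muscular, PNS, CNS, haematological, biological:

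6 + 12 + 4 + 6 + 9 + 15 + 15 + 18 + 15 + 15 + 6 + 2 = 123.

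This is the stated maximum, so the scoring rule is read correctly.

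**Step 2: size of one discordant rating.** Low minus No = 5 × (1 − 0) = 5 points. This is an upper bound. A patient who fails the *due to* wording does not plainly fit the definition of level 0 either, because some active involvement is present. The documents do not give that patient's score, so the gap is 0 to 5.

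**Step 3: who could be discordant.** All of these must hold together:
- the involvement is active and attributed to the disease (damage and unrelated respiratory disease are rated as inactive);
- the radiograph is clear;
- there is no interstitial lung disease (which would reach Low by the other route, or a higher level);
- no Moderate or High criterion is met;
- either cough or bronchial involvement is present in a form that satisfies *or* but not *due to*.

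The documents give no frequency for this combination.

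**Step 4: effect on the change score for such a patient, taking the 5-point bound.**

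| Situation | Difference in change score |
|---|---|
| One wording used throughout, finding present at both visits | 0 |
| One wording used throughout, finding appears or resolves | 5 in absolute value between the two wordings |
| Wording differs between baseline and Week 24, finding stable | spurious −5 or +5 |

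**Step 5: effect on the group comparison, one patient rated differently at only one of the two visits.**
- That arm's raw mean change: 5 / 24 = 0.21 at most.
- Contrast, patient on placebo: 5 / 24 = 0.21 at most.
- Contrast, patient on LOU064: 5 / (2 × 24) = 5 / 48 = 0.10 at most.

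These figures assume 24 observed Week 24 values per arm and precede covariate adjustment. Any one-level change in any weight-5 domain gives the same numbers, so they do not measure this wording in particular.

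**Step 6: stratum and entry.** With muscular, PNS and CNS at 0, an eight-domain baseline score of 5 to 9 gives a total of 5 to 9 without pulmonary Low and 10 to 14 with it. Such a patient can change model stratum. The stratum and the covariate are both fixed before dosing, so a shift in either does not bias the randomised comparison. Eligibility cannot change, because pulmonary is outside the eight entry domains.

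**Step 7: cell against footnote.** The cell has *or* plus a caret. The caret leads to a note that names the domain, the level and the column, and states one wording as the result of the modification. Read together they give one instruction. What is missing is the typed replacement in the cell.

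**The case for a change.** The strongest case for acting is that Section 8.3.1 points to Section 16.4 as the scoring definition, and that definition prints two wordings. Anyone who copied the cell alone into the tablet, the training slides or the scoring program would carry forward the wording that the protocol says it replaced. The footnote itself treats the difference as an inconsistency worth correcting. The remedy would also be cheap: one phrase, and a check that the other materials agree.

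What stands is that the mismatch is real, and that the caret makes the intent clear without making the cell right. What does not follow is any shown effect. The tablet text is not in the documents, and SAP Appendix 5.5.1 is redacted, so there is no evidence that raters saw the cell wording or saw two wordings. If the tablet shows a single wording, raters work from one rule whatever the appendix cell prints. Subjects and investigators are blinded, so a rater's choice between the wordings should not depend on arm. The expected consequence is slightly more rating noise, and the one-arm shifts in Step 5 describe a single invented patient.

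**Conclusion.** The cell and its footnote disagree in print, and the cause is a replacement phrase that was not typed into the table. This is a clerical slip, and no change to the plan follows. The document already states which wording results from its own modification, at the place where a rater would look.

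The bound is 0 to 5 points of total ESSDAI for one discordant rating, in a patient type that is narrowly defined and not shown to exist in this trial. Eligibility is unaffected, equal ratings at both visits cancel, and a shifted baseline covariate or stratum leaves the randomised comparison unbiased. No total effect on the primary contrast can be computed, because the documents give no frequency for such findings.

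The conclusion assumes that raters follow the caret or a tablet with one wording, and that blinding holds. Evidence that raters were shown different wordings would reopen the question, but the documents contain none. Tidying the phrase at a routine revision would do no harm, but it is not shown to alter any rating, result or conclusion.

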**List of abbreviations**

AE	Adverse Event
AUC	Area under the curve
Bid	Twice a day (for latin: "bis in die")
CRF	Case Report Form
CSR	Clinical Study Report
DMS	Document Management System
ECG	Electrocardiogram
EoS	End of Study
EQ-5D	EuroQual 5 dimensions (Standard instrument to measure the health-related quality of life)
ESSDAI	EULAR Sjögren's Syndrome Disease Activity Index
ESSPRI	EULAR Sjögren's Syndrome Patient Reported Index
FACIT-F	Functional Assessment of Chronic Illness Therapy-Fatigue
FAS	Full Analysis Set
IA	Interim Analyses
	Commercially Confidential Information
MedDRA	Medical Dictionary for Drug Regulatory Affairs
MMRM	Mixed effect Model Repeat Measurement
PhGA	Physician global assessment scale
PK	Pharmacokinetics
PPS	Per-Protocol Set
PRO	Patient-reported Outcomes
RAP	Reporting & Analysis Process
SAP	Statistical Analysis Plan
SAS	Statistical Analysis System
SjS	Sjögren's Syndrome
TFLs	Tables, Figures, Listings
ULN	Upper Limit of Normal
WHO	World Health Organization

## 1 Introduction

The purpose of this Statistical Analysis Plan (SAP) is to describe the implementation of the statistical analyses for CCI “*CLOU064E12201*” trial. This SAP will be used in executing the CSR CCI for this study.

Study protocol amendment (v04), IA SAP (v03) and full study SAP (initial) are available at the time of finalization of SAP.

### 1.1 Study design

This is a randomized, double-blind, placebo-controlled, multicenter, CCI study to evaluate the safety and efficacy of multiple LOU064 doses in patients with moderate to severe Sjögren's Syndrome (SjS).

Commercially Confidential Information In CCI the study, the CCI dose (100 mg LOU064) is being tested in two different treatment regimen: *qd* and *bid*, and compared to a Placebo arm. A total of approximately 72 subjects will be equally randomized to these three treatment groups for an expected sample size of 24 subjects per group.

[figure not shown]
Commercially Confidential Information

Commercially Confidential Information

Each individual study subject will first undergo a screening prior of up to 6 weeks, a treatment duration of 24 weeks and a follow-up period of approximately 30 days post last administration of study treatment, before the End of Study (EoS) visit. The total duration for each subject in the study, including screening, will be up to 35 weeks, as shown in Figure 1-2.

Figure 1-2: Study flow chart and visit schedule

Key: B: Baseline; R: Randomization; A: Assessments; P: PK sampling; E: end of treatment

## 1.2 Study objectives, endpoints and estimands

Objective(s)	Endpoint(s)
Primary objective(s)	Endpoint(s) for primary objective(s)

 
Commercially Confidential Information
 
	
 
Change from baseline in ESSDAI at Week 24
 

Secondary objective(s)	Endpoint(s) for secondary objective(s)

 
To evaluate the efficacy of LOU064 compared to placebo with respect to change from baseline on patient and physician-reported outcomes over time
 
	
 
Change from baseline in ESSPRI, FACIT-F, EQ-5D and PhGA over time
 

 
Commercially Confidential Information
 
	
 
Change from baseline in ESSPRI at Week 24
 

 
To evaluate the efficacy of LOU064 compared to placebo with respect to change from baseline in ESSDAI over time
 
	
 
Change from baseline in ESSDAI over time
 

 
To evaluate the safety and tolerability of LOU064
 
	
 
Safety endpoints will include                             
 
Occurrence of treatment emergent adverse events (both serious and non-serious) during the study
 
 
 

Objective(s)	Endpoint(s)

 
To assess PK parameters of LOU064
 
	
 
Occurrence of treatment emergent abnormal vital signs, laboratory and ECG during the study
 
PK parameters AUC, Cmax, Tmax and if feasible MRT and others as needed
 

Exploratory objective(s)	Endpoint(s) for exploratory objective(s)

Commercially Confidential Information

### 1.2.1 Primary estimand(s) CCI

The following estimand framework is adopted for the primary analysis CCI .

- Population: The subjects in the FAS; data up to Week 24 visit are included.
- Variable of interest: Change from baseline in ESSDAI total score after 24 weeks of study drug administration. This will be defined as the Week 24 visit ESSDAI value minus the baseline ESSDAI value with negative values indicating improvement in disease status.
- Treatment of interest: The randomized treatment (LOU064 or placebo) on top of allowed concomitant medication
- Intercurrent events: Regardless whether early termination from the study, interruption of study treatment, or intensified concomitant treatment (local and systemic) has occurred
- Summary measure: Difference in mean change from baseline in ESSDAI total score at Week 24 visit between placebo and LOU064 (100mg *qd* and *bid* averaged).

## 2 Statistical methods

### 2.1 Data analysis general information

Blinded analyses using dummy treatment codes will be produced by ClinBAY statisticians and programmers according to this SAP, using SAS version 9.4 or higher (SAS Institute, Cary NC). Programs and datasets will then be provided to and run by ClinBAY Statistician and Programmer using the true treatment codes to provide the unblinded TLFs in electronic format for discussion. Details of these analyses are outlined in this document.

